5.5. Interim Analysis and Data Monitoring

5.5.1. Data Monitoring Committee

The Data Monitoring Committee (DMC) will review the progress of the study and will monitor participant intake, outcomes, adverse events, and other issues related to participant safety. The DMC makes recommendations to the Director of the Clinical Science Research and Development (CSRD) Service about whether the study should continue or be stopped. The DMC will consider safety or other circumstances as grounds for early termination, including either compelling internal or external evidence of treatment differences or the unfeasibility of addressing the study hypothesis (e.g., poor participant intake, poor adherence to the protocol). In general, this committee meets at six to nine months after the start of subject recruitment and yearly thereafter. The committee will receive reports about two weeks prior to their annual meetings and at six monthly intervals in between the annual meetings.

5.5.2. Planned Schedule of Interim Analysis and Stopping Rules

There will be three interim analyses of the primary outcome measure performed in the study when 25%, 50%, 75% of the planned participants completed their participation in the study. If analysis of the primary outcome rates at the time of interim analysis indicates that the null hypothesis can be rejected the study will be recommended for termination for safety reasons. A Haybittle-Peto interim analysis is proposed where a Z-statistic is computed and if it should exceed the critical value of 4.0 then the committee should recognize that an important “warning” has been made and that a decision is indicated (Appendix 4).

6. SUMMARY OF STUDY DATA

6.1. Subject Disposition

Subject disposition will be summarized for all participants that signed the consent form and for the ITT population. The following data will be presented:

- A CONSORT diagram including the overall number of screened, eligible, consented, and randomized (Figure 1).
- A figure of participants randomized and expected by month (Figure 2).
- Summary of screening, consenting, and randomization by site (Table 1).
- Reasons of ineligibility for consent and consent information by site (Table 2)

- Reasons of ineligibility for randomization by site (Table 3).
- Reasons of eligible participants not randomized by site (Table 4).
- Participant disposition by sites for all randomized participants (Table 5).
- Participant disposition by intervention group for all randomized participants (Table 6).
- A list of participants who are administratively terminated (Table 6.1).
- A list of participants whose termination reasons are listed as ‘Other’ (Table 6.2).

6.2. Study Adherence

The following tables will be presented:

- Summary of protocol deviations by intervention (Table 7).
- Summary of approved transfusion protocol halting by site (Table 8).
- Summary of transfusion-related protocol deviations by site (Table 9).

6.3. Subject Demographics

Subject demographics will be summarized by intervention group, and for all participants (ITT and mITT; Tables 10a-b). The subject demographics such as age, race, gender, ethnicity, will be analyzed. For continuous variables, the sample size, mean/SD or median/interquartile range, minimum, and maximum values will be calculated and the difference between the intervention groups will be tested either by Student t or Wilcoxon rank sum test depending on data distributions. For categorical variables, the number and percentage of participants by center or the intervention group will be tabulated and the difference between the intervention groups will be tested using Pearson chi-square test.

Age will be calculated as the number of years between the participant’s birth date and randomization date.

6.4. Baseline Characteristics

Baseline comparability among the intervention groups will be evaluated with respect to baseline characteristics including height, weight, BMI, pre-operative hemoglobin, albumin, creatinine, SBP/DBP, RCRI class besides the demographic variables including BMI. The

sample size, mean, median, SD, minimum, and maximum values for the continuous measures and the number and percentage for the categorical variables will be summarized for each intervention group and all participants (Tables 11a-b).

Weight at screening from physical examination CRF will be used for the summary.

BMI = (Weight/Height²)*100². The unit of weight will be kilogram and the unit of height will be centimeter.

6.5. Medical History

The number and percentage of participants reporting a medical history will be summarized by the following medical conditions: Hypertension, hyperlipidemia, coronary artery disease, congestive heart failure, COPD or previous active TB, dementia or current change in mental status, MI within 6 months, malnourished or cachectic, cancer or current chemotherapy, immunodeficiency or infection with HIV, ischemic stroke or TIA, prior coronary stent, cardiac arrhythmias, MI older than 6 months, end stage renal disease, prior coronary bypass, diabetes treated with medications (oral hypoglycemic or insulin), past smoking, and current smoking (Tables 12a-b).

6.6. Pre-admission Ambulation and Residence

The number and percentage of participants in each pre-admission ambulation category and residence status will be summarized as in Tables 13a-b.

6.7. Pre/Post-Admission Medications

Pre/after admission medications are recorded in this study. Each summary below will be done for each intervention group and for all participants:

- Prior medications – Prior medications are collected for those randomized patients before their admission (Tables 14a-b)
- Current medications – Current medications are medical orders for those randomized patients during their hospital stay at the day before the index operation, operation day, the day after the operation, two days after the operation, and discharge day. The

number and percentage of participants who are prescribed these medications on each of the above days will be summarized (Tables 15a-b).

7. EFFICACY ANALYSES

The primary analysis of the study will be performed on the primary endpoint on the ITT population. The secondary analyses will be performed on the secondary and tertiary endpoints on the ITT population, as well as the analyses performed on all the primary, secondary, and tertiary endpoints on the mITT, No-Recent-Transfusion, Completers, and Per Protocol populations unless otherwise specified. Potential difficulties of convergence of model fit, which may arise in efficacy analyses that include covariates, will be handled using the method described in Section 7.1.

7.1. Primary Endpoint Analysis

The primary study endpoint will be a composite outcome of all-cause mortality, MI, coronary revascularization, acute renal failure, or post-randomization stroke within 90 days from randomization. A clinical events committee will adjudicate all component events for the primary endpoint. The number and percentage of participants with the composite endpoint at the 90-day visit after the randomization will be summarized and compared according to assigned transfusion strategy (analysis by intent to treat) using Pearson χ^2 test. Another analysis will compare primary endpoint between the two transfusion strategies stratified by clinical sites using the Cochran-Mantel-Haenszel test (Table 16a-e). The test for differences between transfusion strategies in the primary outcome will be conducted at an overall α -level of 0.05. Additional analysis will be conducted using logistic models to adjust for other clinical factors, such as age, RCRI, and nadir Hb. The interactions of the intervention with age, RCRI and nadir Hb will also be considered.

Odds ratio and 95% confidence interval (CI) will be presented using SAS PROC GENMOD or PROC LOGISTIC. Assumptions of the model including linearity in the logit of the composite event risk for continuous variables will be checked. We will assess goodness-of-fit using the statistic -2 log likelihood, which has a chi-square distribution under the null hypothesis that all the explanatory variables in the model are not associated with the outcome

variable. We will also consider the Akaike Information Criterion statistic and the Schwartz Criterion statistic, both of which adjust the -2 log likelihood for the number of items in the model. Models that show lack of fit will be reconsidered for the inclusion of additional variables or use of alternate models with assumptions that are better met by the study data. One alternate model if the model fit is poor for logistic regression is a log-linear model. For logistic regression analysis, if the coefficient for intervention effect is significant (i.e., the confidence interval for the odds ratio does not include 1), then the null hypothesis of no intervention effect adjusting for other covariates in the final model will be rejected. The P value for testing each covariate coefficient in the model being zero will be based on Wald test (Table 17a-e). The primary analysis will be done in the ITT population. Additional analyses will be done in the mITT, No-Recent-Transfusion, Completers, and Per Protocol populations.

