After an eligible participant provides informed consent, the study staff will complete all sections of the pre-randomization forms except for the postoperative Hb measurements. The clinical site coordinator will be responsible for tracking the postoperative Hb levels and identifying participants whose Hb level is below 10 gm/dl and therefore eligible for randomization. iStat hemoglobin values may not be used as the basis for randomization/transfusion decisions. The CSPCC staff will prepare randomization schedules for each clinical site participating in the study. The study randomization to either liberal or restrictive transfusion policy will be done by an Interactive Touchtone Telephone Randomization System (ITTRS). A stratified block randomization scheme will be used to randomize participants in the two transfusion groups. The stratifying factors are clinical site and revised cardiac risk index (RCRI) class. Following participant randomization, clinical data and transfusion records will be obtained by the study team.

C. Participant Assessments

1. Baseline Assessment

Baseline assessments will be collected the time between identification of an eligible participant and either randomization or 15 days after surgery (or until discharge, whatever comes first) including revised cardiac risk index (RCRI), patient history, hemoglobin level, EKG diagnosis, troponin, serum creatinine, albumin, and patient clinical status. Data collected during this period is used primarily for monitoring recruitment and randomization status. We will maintain the information of all identified potential participants. This will be accomplished by completing the screening form for every participant presenting to the clinical site for eligible operations including those who are excluded from the study for any reason. Following is a list of assessments that we plan on collecting:

Screening Record: To compare patient screened (but not randomized) to patient randomized in this study, a comprehensive screening assessment will be completed for all potentially eligible subjects scheduled to receive an open surgery procedure at a participating center by the Study Coordinator.

Demographic: The clinical site coordinator will collect demographic and participant information. The demographic information will include participant's age, gender, race, marital status, etc.

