The primary study endpoint will be composite outcome of all-cause mortality, MI, coronary revascularization, acute renal failure, or post-randomization stroke within 90 days from randomization. This outcome will be compared according to assigned transfusion strategy (analysis by intent to treat), using Pearson χ^2 test. The test for differences between transfusion strategies in the primary outcome will be conducted at an overall α -level of 0.05. Additional analysis will be conducted using logistic models to adjust for other clinical factors, such as age, RCRI, nadir Hb, and interaction terms. Logistic regression will be used for the primary endpoint ($y = 1$ if a composite outcome, otherwise $y = 0$) analysis with transfusion strategy group as the testing factor (X). The following covariates will be included in the model: age (z_1), RCRI (z_2), nadir Hb(z_3), site (z_4), and the interactions of testing factor with age (w_1), RCRI (w_2) and nadir Hb (w_3). Given the composite outcome probability $p = \Pr(y=1|X, z_1, z_2, z_3, z_4, w_1, w_2, w_3)$, the basic model is defined as follows:

$$\text{Logit}(p) = \ln\left(\frac{p}{1-p}\right) = \beta_0 + \beta_1 X + \beta_2 z_1 + \beta_3 z_2 + \beta_4 z_3 + \beta_5 z_4 + \beta_6 w_1 + \beta_7 w_2 + \beta_8 w_3$$

Odds ratio and 95% confidence interval (CI) will be presented using SAS PROC GENMOD. If the coefficient for treatment effect is significant, then the null hypothesis will be rejected. Logistic models will be tested for goodness of fit. We will assess goodness-of-fit using the statistic -2 log likelihood, which has a chi-square distribution under the null hypothesis that all the explanatory variables in the model are zero. We will also consider the Akaike Information Criterion statistic and the Schwartz Criterion statistic, both of which adjust the -2 log likelihood for the number of items in the model. Models that show lack of fit will be reconsidered for the inclusion of additional variables or use of alternate models with assumptions that are better met by the study data. One alternate model if model fit is poor for logistic regression is a log-linear model.

3. Secondary endpoint analyses

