Other Analyses 1. Baseline characteristics 2. Disposition status 3. Adherence 4. Age of Blood in relation to 90 day composite endpoint, wound Infection, and pneumonia 5. Time-to-event analyses for primary and secondary endpoints	1. Student t or Wilcoxon test, Pearson chi-square or Fisher test, 2. Pearson chi-square test 3. Pearson chi-square test 4. Pearson chi-square tests and Logistic regression 5. Log-rank test and Cox regression	1. PROC TTEST, PROC FREQ, PROC NP1WAY 2. PROC FREQ 3. PROC FREQ 4. PROC FREQ, PROC GENMOD 5. PROC LIFETEST, PROC PHREG

F. Criteria for Study Termination

There will be three interim analysis of the primary outcome measure performed in the study when 25%, 50%, 75% of the planned participants completed their participation in the study. If analysis of the primary outcome rates at the time of interim analysis indicates that the null hypothesis can be rejected the study will be recommended for termination for safety reasons.

G. Handling of Missing Data

Every effort will be made to minimize the occurrence of missing data, particularly for the primary and main secondary outcome measures. For the primary outcome, every effort will be made to contact the participants over the phone until participant termination. In the event of a potential drop out, every effort will be made to capture the primary outcome data from the VA databases. For participants who drop out during the study, multiple imputation (MI) method may be used for certain endpoint analyses. Multiple imputations will be based on Rubin's procedure using SAS PROC MI and PROC MIANALYZE. Sensitivity analysis will be performed to compare the results from the imputed data and the complete data without imputation.

H. Reporting of Any Deviations from the Original Statistical Plan

A more detailed statistical analysis plan (SAP) will be generated which will include the details of each statistical analysis plan for each outcome measure along with the suggested table shells for any reports that will be produced during the study and at the end of the study. Any deviations in the statistical plan from the protocol will be specified in the SAP. Any deviations from the SAP will be specified in a revised main manuscript which will be prepared and published at the end of the study.

XVII. STUDY ORGANIZATION AND ADMINISTRATION

A. Requirements for Participating Medical Centers

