4.3. Randomization and Blinding

The clinical site coordinator will track the participants' postoperative Hb levels and identify participants whose Hb level is below 10 gm/dl and therefore eligible for randomization. iStat hemoglobin values may not be used as the basis for randomization/transfusion decisions. The CSPCC staff will prepare randomization schedules for each clinical site participating in the study. The study randomization to either liberal or restrictive transfusion policy will be done by an Interactive Touchtone Telephone Randomization System (ITTRS). A stratified block randomization scheme with block sizes of 2 and 4 will be used to randomize participants in the two transfusion groups. The stratifying factors are clinical site and revised cardiac risk index

(RCRI) class. The participants and the Endpoint Committee will be unaware of treatment group allocation.

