Other oral anticoagulant	n (%)			

Table 15a-b. Post-admission Medications (ITT, mITT)

Status	Statistics	Liberal Arm (N =)	Restrictive Arm (N =)	Total (N=)
Post-admission Medications				
Coumadin	n/N (%)			
Day 1 pre-op				
Op day (before or after Op)				
Day 1 post op				
Day 2 post-op				
Discharge day				
Any of the days				

Status	Statistics	Liberal Arm (N =)	Restrictive Arm (N =)	Total (N=)
Heparin Day 1 pre-op Op day Day 1 post op Day 2 post-op Discharge day Any of the day	n/N (%)			
LMW Heparin Day 1 pre-op Op day Day 1 post op Day 2 post-op Discharge day Any of the days	n/N (%)			
Oral Anticoagulant other than Coumadin Day 1 pre-op Op day Day 1 post op Day 2 post-op Discharge day Any of the days	n/N (%)			
Aspirin Day 1 pre-op Op day Day 1 post op Day 2 post-op Discharge day Any of the days	n/N (%)			
Beta-Blocker Day 1 pre-op Op day Day 1 post op Day 2 post-op Discharge day Any of the days	n/N (%)			
Plavix Day 1 pre-op Op day Day 1 post op Day 2 post-op Discharge day Any of the days	n/N (%)			

Status	Statistics	Liberal Arm (N =)	Restrictive Arm (N =)	Total (N=)
Diuretics Day 1 pre-op Op day Day 1 post op Day 2 post-op Discharge day Any of the days	n/N (%)			
ACE Inhibitor Day 1 pre-op Op day Day 1 post op Day 2 post-op Discharge day Any of the days	n/N (%)			
Insulin Day 1 pre-op Op day Day 1 post op Day 2 post-op Discharge day Any of the days	n/N (%)			
Oral Hypoglycemics Day 1 pre-op Op day Day 1 post op Day 2 post-op Discharge day Any of the days	n/N (%)			
Other Immunosuppressant Day 1 pre-op Op day Day 1 post op Day 2 post-op Discharge day Any of the days	n/N (%)			
Prednisone Day 1 pre-op Op day Day 1 post op Day 2 post-op Discharge day Any of the days	n/N (%)			

Status	Statistics	Liberal Arm (N =)	Restrictive Arm (N =)	Total (N=)
Statin	n/N (%)			
Day 1 pre-op				
Op day				
Day 1 post op				
Day 2 post-op				
Discharge day				
Any of the days				

Note: Medications on operation day does not include intraoperative medications

Table 16a-e. Primary Endpoint Analysis (ITT, mITT, No-Recent-Transfusion, Completers, Per-Protocol)

Results	Liberal (n =)	Restrictive (n =)	All Subjects (N=)
	n (%)	n (%)	n (%)
Composite event (Yes)			
Composite event (No)			
Total			
Pearson χ^2 test			
Cochran-Mantel-Haenszel test	(p =) Stratified on Clinical Centers		

Table 17a-e. Primary Endpoint Analysis, Adjusting for Baseline Age, RCRI, and Nadir Hemoglobin (ITT, mITT, No-Recent-Transfusion, Completers, Per-Protocol)

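### Randomisation is stratified by site and RCRI class, but no named SAP analysis uses both, and the SAP drops the protocol's site term and loosens its interaction terms without saying so (minor)

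*SAP*

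**What the plan says.** **Design.** Protocol IX.B: "The stratifying factors are clinical site and revised cardiac risk index (RCRI) class". SAP 4.3 repeats this and gives block sizes of 2 and 4.

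**SAP analyses.**
- Primary (7.1): the composite is "summarized and compared according to assigned transfusion strategy (analysis by intent to treat) using Pearson" chi-square, unstratified.
- Supportive (7.1): a comparison "stratified by clinical sites using the Cochran-Mantel-Haenszel test (Table 16a-e"), so site without RCRI.
- Logistic models (7.1-7.3), quantile regression (7.2), and age-of-blood and Cox models (7.4): age, RCRI and nadir Hb, without site. Table 17 is titled "Primary Endpoint Analysis, Adjusting for Baseline Age, RCRI, and Nadir Hemoglobin". Shells 17, 19, 21 and 23-28 have no site row.
- Interactions of treatment with age, RCRI and nadir Hb: 7.1 says only that they will be considered, and Table 17 has no rows for them.

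**Protocol XVI.E.** The primary logistic model lists "nadir Hb(z_3), site (z_4") among its covariates and fixes the three treatment interactions in the equation. Site is also named in the text for the secondary binary, age-of-blood and Cox models. Table 4 names site and the interactions for every primary, secondary and tertiary regression. The protocol's own text for the quantile and tertiary models leaves site out, against Table 4.

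**Commitment.** Protocol XVI.H: "Any deviations in the statistical plan from the protocol will be specified in the SAP".

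**The concern.** Blocking within prognostic strata makes the arms more alike than simple randomisation would. A test that ignores the strata does not credit that balance: its standard error is slightly too large, its confidence interval slightly too wide, and its true type I error slightly below nominal. The usual remedy is to analyse by the factors used to randomise. Here one factor appears in the CMH test and the other in the regressions, never both together.

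The second issue is pre-specification. For the same endpoints the two governing documents give different adjusted models, in site and in interactions, with no reason stated. Whoever runs the final analysis would have to choose between them.

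**Working it through.** **1. The plan's sample size.** With 30% vs 22.5%, pooled rate 0.2625, two-sided 5% and 90% power:

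n per arm = [1.96·√(2·0.2625·0.7375) + 1.2816·√(0.30·0.70 + 0.225·0.775)]² / 0.075² = (1.2196 + 0.7946)² / 0.005625 = 721.2

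This rounds to 722 per arm, or 1444, and 1444/0.95 = 1520. Both match SAP 4.5. The unstratified Pearson test is the basis of the sample size.

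**2. How prognostic the strata are.** The RCRI odds ratios are 1, 1.8, 2.07 and 2.38, from the single-institution series in Protocol II(b). The documents give neither the RCRI mix nor the between-site variation, so both are assumed: equal classes or a 10/40/30/20 mix, and a normal site effect with SD 0, 0.3 or 0.5 on the logit. With the intercept solved so that the overall risk p is 0.2625:

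R² = Var(stratum risk) / [p(1−p)], and R²s is the part due to site alone.

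**3. Consequences under blocking by site and RCRI.**
- Pearson alpha = 2[1 − Φ(1.96/√(1−R²))]
- Pearson power = Φ(1.2816/√(1−R²))
- Site × RCRI power = Φ(3.2416/√(1−R²) − 1.96)
- CMH-by-site power = Φ{(3.2416/√(1−R²s) − 1.96)·√[(1−R²s)/(1−R²)]}

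Example, equal mix and SD 0.3: R² = 0.0341, so √(1−R²) = 0.9828. Pearson alpha = 2[1 − Φ(1.994)] = 4.61%, Pearson power = Φ(1.304) = 90.39%, and site × RCRI power = Φ(3.298 − 1.96) = 90.96%.

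| Mix | Site SD | R² % | Pearson alpha % | Pearson power % | CMH site % | Site × RCRI % |
|---|---|---|---|---|---|---|
| Equal | 0 | 1.78 | 4.80 | 90.20 | 90.20 | 90.50 |
| Equal | 0.3 | 3.41 | 4.61 | 90.39 | 90.66 | 90.96 |
| Equal | 0.5 | 6.10 | 4.31 | 90.70 | 91.42 | 91.70 |
| 10/40/30/20 | 0 | 0.85 | 4.90 | 90.10 | 90.10 | 90.24 |
| 10/40/30/20 | 0.3 | 2.52 | 4.71 | 90.29 | 90.57 | 90.71 |
| 10/40/30/20 | 0.5 | 5.28 | 4.40 | 90.60 | 91.34 | 91.48 |

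Over Pearson the gain is 0.15-1.00 points, worth 7-54 of 1444 participants, with a confidence interval 0.4-3.1% narrower (1 − √(1−R²)). Over the planned CMH by site it is 0.14-0.30 points, worth about 8-16 participants.

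**4. Simulation checks.**
- 16 assumed sites of 4 to 252 participants, 10,000 trials per setting, site cells under 10 combined within RCRI class. The site × RCRI CMH gained 0.20-0.88 points over Pearson (SE 0.07-0.10) and 0.05-0.34 over CMH by site (SE 0.08-0.09). Null rejection was 4.5-5.3% for Pearson and 5.0-5.5% for the pooled CMH (SE 0.22).
- 15 equal sites, site SD up to 0.6, 2,500-3,000 trials per setting. Logistic regression on arm, site and RCRI gained about 0.4-1.5 points over Pearson. The unpooled site × RCRI CMH differed from CMH by site by −0.04 to +0.13 points.

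Both agree that the gain is small and that most of what site offers is already captured by the planned CMH.

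**5. Site as a fixed effect for rare components.** Protocol Table 2 gives coronary revascularisation as 0.4% and 0.3% in the two nadir-Hb groups: 760·0.004 + 760·0.003 ≈ 5 events. With 15 equal sites, 15·(14/15)^5.3 ≈ 10 would have none. Stroke at about 1% (Protocol II(c)) gives about 15 events, and 15·(14/15)^15.2 ≈ 5 sites with none. Fixed site terms would then cause separation.

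**The case against.** The strongest reply is that Pearson is valid, is named in the protocol, matches the sample-size basis, and errs on the conservative side. Each factor already enters a pre-specified primary-endpoint analysis: site in the CMH, RCRI in the logistic model. This stands, and it is why the point is minor.

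A reader might infer that the primary test should be replaced. The documents do not support that. The gain over an analysis already planned is at most 0.30 points in closed form and near zero in some simulated settings. The interim rule in SAP 5.5.2 ("A Haybittle-Peto interim analysis is proposed where a Z-statistic is computed and if it should exceed the critical value of 4.0") is built on a Z-statistic at three looks. The documents do not say whether a look has taken place, so a change of test could leave interim and final statistics unmatched.

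It can also be said that the covariate list in SAP 7.1 is open-ended and that variables may be added for poor fit. That permits site but does not specify it. Table 17 closes the list without it, and the lists in 7.2-7.4 are not open-ended.

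Sparse sites might explain why site was dropped, but no such reason is given. SAP 7 refers to 7.1 for a way of handling convergence problems, and 7.1 contains none. Finally, the SAP's opening pages were not in the copy reviewed, so non-declaration is confirmed only for the text available, which includes numbered sections 1 to 8.

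**Conclusion.** The point holds as a minor one. No named analysis in the available SAP uses both stratification factors. The SAP omits site from models where the protocol includes it, and weakens the protocol's fixed interactions to an option, without declaring either. These documentary findings rest on no assumption. For the quantile and tertiary models the protocol contradicts itself on site, so the SAP cannot agree with both places.

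The statistical cost is small: Pearson alpha about 4.3-4.9% in closed form, and 0.15-1.0 power points against Pearson or 0.14-0.30 against the planned CMH. These ranges depend on the assumed RCRI mixes, site SD of 0 to 0.5, and RCRI odds ratios from one vascular series. The simulated null rates are too noisy to confirm or refute conservatism of this size.

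Two further inferences should be resisted. One is that ignoring the strata inflates type I error or leaves the trial underpowered: the direction is the opposite, and power stays at or above 90%. The other is that putting site back would bring the two documents into line: the interaction terms would still differ, and the lack-of-fit clause in both documents would still let the model change.

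**What to change.** Before unblinding:

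1. Keep Pearson as the primary test. Extend the supportive CMH in SAP 7.1 from site to site and RCRI class, and report the matching stratified risk difference with its 95% CI. Fix a sparse-cell rule now, blind to arm: for example, within each RCRI class, combine all site cells with fewer than 10 randomised, counting both arms together. The interim Z-statistic need not change.
2. Restore site in the SAP primary, secondary, age-of-blood and Cox models, or declare its removal and give the reason. For coronary revascularisation and stroke, avoid fixed site effects: use the stratified CMH with pooled cells, or a conditional or penalised model.
3. Reconcile the interaction terms between the protocol's primary model and Table 4 on one side and SAP 7.1-7.4 and their shells on the other. Reconcile the protocol's text for the quantile and tertiary models with Table 4.
4. Optionally add a supportive model with treatment, site and RCRI only. Protocol XVI.A expects nadir Hb to depend on arm, so models that include it do not give a clean stratified estimate.

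The cost is wording in SAP 7.1-7.4 and changes to the affected shells (16, 17, 19, 21, 23-28). The protocol's internal mismatch can be corrected there or settled by a statement in the SAP. Both factors are known at randomisation, so no data need to be collected.
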